6.0 STUDY TREATMENT

Study treatment is defined as any investigational drug(s), marketed product(s), placebo, or medical device(s) intended to be administered to a patient according to the study protocol.

6.1 Study Treatment(s) Administered

Table 3 Study Treatment Details

Study Treatment Name:	ATI-450	Placebo
Dosage Formulation:	Tablet	Tablet
Unit Dose Strength(s)/Dosage Level(s):	50 mg BID	Not applicable
Route of Administration	Oral	Oral
Dosing Instructions:	Take 1 tablet by mouth BID	Take 1 tablet by mouth BID
Packaging and Labeling	[REDACTED]	[REDACTED]
Manufacturer	[REDACTED]	[REDACTED]

Abbreviation: BID=twice daily

6.2 Preparation/Handling/Storage/Accountability

The Investigator or designee must confirm appropriate temperature conditions have been maintained during transit for all study treatment received and any discrepancies are reported and resolved before use of the study treatment.

ATI-450 and placebo will be stored under controlled conditions according to the storage requirements described on the label(s). [REDACTED]

[REDACTED] The Investigator (or designee) will instruct patients to store the study treatment in accordance with the instructions on the label(s).

Only patients enrolled in the study may receive study treatment and only authorized study center staff may supply or administer study treatment. All study treatments must be stored in a secure, environmentally controlled, and monitored (manual or automated) area in accordance with the labeled storage conditions with access limited to the Investigator and authorized study center staff.

The Investigator and/or designee is responsible for study treatment accountability, reconciliation, and record maintenance (ie, receipt, reconciliation, and final disposition records).

The Investigator, a member of the study center staff, or a hospital pharmacist must maintain an adequate record of the receipt and distribution of all study treatment using the Drug Accountability Form. These forms must be available for inspection at any time.

Additional instructions regarding study treatment preparation and handling and the final disposition of unused study treatment can be found in the Pharmacy Manual.

6.3 Measures to Minimize Bias: Randomization and Blinding

All patients will be centrally assigned to randomized study treatment using an Interactive Voice/Web Response System (IxRS). Before the study is initiated, access instructions and directions for the IxRS will be provided to each study center.

Study treatment will be dispensed at the study visits summarized in the SoA ([Table 1](#)). Refer to the study Pharmacy Manual for specific guidelines concerning dispensing and accountability procedures for study treatment.

Patients will be randomized to study treatment in a 1:1 ratio to ATI-450 50 mg BID or placebo.

This is a double-blind study with limited access to the randomization code. The ATI-450 and placebo tablets will be identical in physical appearance. The treatment each patient will receive will not be disclosed to the Investigator, study center staff, patient, or Sponsor/designee. The treatment codes will be available to a limited number of third-party vendor personnel (IxRS administrative personnel, Clinical Supplies Management personnel, and unblinded biostatistician) for them to support their functions on the study.

The IxRS will be programmed with blind-breaking instructions. In case of an emergency, the Investigator has the sole responsibility for determining if unblinding of a patient's treatment assignment is warranted. Patient safety must always be the first consideration in making such a determination. If the Investigator decides that unblinding is warranted, the Investigator should make every effort to contact the study Medical Monitor prior to unblinding a patient's treatment assignment unless this could delay emergency treatment of the patient. If a patient's treatment assignment is unblinded, the study Medical Monitor must be notified within 24 hours after breaking the blind. The date and reason that the blind was broken must be recorded in the source documentation and electronic case report form (eCRF), as applicable.

6.4 Study Treatment Compliance

The prescribed dosage, timing, and mode of administration may not be changed. Any departures from the intended regimen must be recorded in the eCRFs.

At each visit, prior to dispensing study treatment, previously dispensed study treatment will be retrieved by the Investigator and compliance assessed both through tablet counting and review of a dosing diary completed by the patient. Patients exhibiting poor compliance as assessed by tablet counts and diary completion should be counseled on the importance of good compliance to the study dosing regimen.

Noncompliance is defined as taking <80% or >120% of study treatment during any evaluation period (visit to visit). See [Section 8.4](#) regarding treatment of ATI-450 overdose.

6.5 Concomitant Therapy

Any medication or vaccine (including over-the-counter or prescription medicines, vitamins, and/or herbal supplements) that the patient is receiving at the time of enrollment (within 14 days before the time of enrollment) or receives during the study must be recorded on the eCRF along with:

- Reason for use;
- Dates of administration including start and end dates and times (if available); and
- Dosage information including dose and frequency.

The Medical Monitor should be contacted if there are any questions regarding concomitant or prior therapy.

Antibiotic Therapy

[figure not shown]
Patients are allowed to continue treatment with antibiotics for HS from the tetracycline class if at stable dose. A stable dose is defined as no change for 4 weeks prior to Baseline visit. The patient must be willing and able to maintain stable dose for duration of study. Allowable oral and topical antibiotics from the tetracycline class are: tetracycline, doxycycline, or minocycline.

Antiseptic Use

If previously used prior to entry into the study, patients may continue cleansing HS lesions with their daily antiseptic wash, such as chlorhexidine gluconate, triclosan, benzoyl peroxide, or dilute bleach in bathwater. Use of new antiseptic wash during the study is not permitted.

Wound Care

Concomitant use of wound care dressings on HS wounds is allowed (excluding topical antibiotics and other prohibited medications).

[REDACTED]

[REDACTED]

[REDACTED]

[REDACTED]

6.5.1 Rescue Medicine

Rescue therapy for HS is not permitted except for the use of acetaminophen (as per label) and nonsteroidal anti-inflammatory drugs to treat breakthrough pain and discomfort during the study. Neither the study center nor the Sponsor will supply rescue medication.

6.6 Dose Modification

No dose modifications are permitted in this study.

6.7 Treatment after the End of the Study

The Sponsor will not provide any additional care to patients after they leave the study because such care should not differ from what is normally expected for patients with HS.

7.0 DISCONTINUATION OF STUDY TREATMENT AND PATIENT DISCONTINUATION/WITHDRAWAL

[figure not shown]
7.1 Discontinuation of Study Treatment

Criteria for discontinuation due to abnormal liver function, neutrophil laboratory values, CK laboratory values, and skin toxicity are outlined below. In the event that a patient discontinues treatment with study treatment prematurely, it is preferred (so as to minimize missing data) that the patient be given the opportunity to complete the remainder of his/her expected study visits per the SoA (Table 1) rather than being discharged from the study in full.

7.1.1 Liver Function

Study intervention will be discontinued for a patient if liver chemistry stopping criteria are met and confirmed upon repeat testing. Samples for confirmation testing should be collected as soon as possible after receipt of initial laboratory results indicative of the need to monitor for stopping criteria. If ALT or AST is $\geq 5 \times$ ULN, then study treatment should be held while confirming.

Liver Chemistry Stopping Criteria and Increased Monitoring Algorithm

Abbreviations: ALT=alanine transaminase; AST=aspartate transaminase, INR=international normalized ratio; SAE=serious adverse event; Tbili=total bilirubin, ULN=upper limit of normal.

Note: The red star indicates the starting point.

Liver Safety: Suggested Actions and Follow-up Assessments can be found in [Appendix 7](#).

7.1.2 Neutrophil Laboratory Values

Withdraw study treatment if absolute neutrophil count drops below 500 cells/mm³ and is maintained below 500 cells/mm³ on a confirmatory sample.

7.1.3 Creatine Kinase Laboratory Values

Withdraw study treatment if an elevation of CK $>5 \times$ ULN is observed on repeat testing without benign explanation (eg, recent exercise) occurs.

7.1.4 Skin Toxicity

Withdraw study treatment in the case of any severe skin reaction which is considered to be related to the study treatment.

If drug is stopped for reasons as described above, restarting the study drug is not allowed.

7.2 Temporary Discontinuation

7.2.1 Unrelated Adverse Events or COVID-19 Diagnosis

If a drug is stopped temporarily due to a clearly unrelated adverse event, for example, treatment of a fracture caused by a motor vehicle accident or COVID-19 infection, dosing may be reinitiated, after discussion with the Medical Monitor, if the temporary discontinuation was shorter than a maximum of 14 days in the total 12-week treatment period. In exceptional circumstances, medical monitor may allow dosing to be resumed with a gap of up to 21 days. In all cases, if the dosing gap is in excess of 21 days, dosing should be discontinued permanently.

In case of a COVID-19 infection, consult study Medical Monitor to discuss risk/benefit considerations of patient continuing or discontinuing study medication treatment.

7.2.2 ECG Criterion for Drug Discontinuation

In the event that a study ECG assessment demonstrates either of the bulleted criteria below (upon local review by the Investigator), a PK and lab sample (serum potassium and magnesium levels) should be drawn. The ECG should be repeated within 30 minutes. Patient study treatment dosing should be interrupted until the results of the centrally read cardiologist report are received and the study Medical Monitor should be notified:

- QTcF (average of triplicate set) >500 msec
- Change from Baseline QTcF (average of triplicate set) >60 msec

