#### **5.5.1. Adverse Events**

Adverse events (AE) will be mapped to a PT and system organ classification (SOC) using MedDRA version 24.0.

An overall summary will be presented which includes the number of TEAEs and the number and percentage of patients who experienced at least one TEAE. This summary will also include:

- Any TEAE
- Any Serious TEAE
- Any Mild TEAEs
- Any Moderate TEAEs
- Any Severe TEAEs
- Any Related TEAEs (defined as Probably or Possibly Related)
- Any TEAEs leading to discontinuation of study drug
- Any Related TEAEs leading to discontinuation of study drug

- Commonly occurring TEAEs (defined as those AEs occurring in  $\geq 10\%$  of ATI-450 patients)

Adverse events of special interest (AESI) are captured on the AE eCRF page and include the following events: mouth ulceration, severe skin reaction which is considered to be related to the study drug, confirmed creatine kinase (CK)  $> 5X$  ULN without benign explanation, absolute neutrophil count  $< 1000$  cells/mm^3, and QTcF  $> 500$  msec or change from baseline QTcF  $> 60$  msec.

Additional summaries of TEAEs will be provided showing the number and percentage of patients who experienced at least one TEAE. These summaries will be presented by SOC and PT. If a participant reports the same PT multiple times within the same SOC, that PT will only be counted once within that SOC for that participant. As with the PT, if a participant reports multiple conditions within the same SOC, that SOC will only be counted once for that participant. In the summary, SOC will be listed in ascending alphabetical order; PTs will be listed in order of descending frequency for all participants within each SOC.

The occurrence of TEAEs related to study medication, TEAEs leading to discontinuation of study drug, study drug related TEAEs leading to discontinuation, AESIs, and serious adverse events (SAEs) will be tabulated by SOC and PT. An additional summary of TEAEs will be provided by SOC, PT and maximum severity. Most frequent TEAEs, defined as AEs occurring in 10% of ATI-450 patients, will be summarized by PT.

All AEs reported will be listed by individual subject, showing both verbatim and PT. All AEs reported with a start date prior to the initiation of study medication will be excluded from the TEAE tables but will be included in the listings.

Missing onset dates will be imputed as previously outlined in [Section 3.3.5](#) as required to determine TEAEs.

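### Protocol 7.2.2 holds dosing for a prolonged QTcF until the central read arrives, but does not say which result allows dosing to resume or requires a stop

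*Protocol*

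**What the plan says.** Protocol 7.2.2 applies when the Investigator's local review finds a triplicate-average QTcF above 500 msec, or more than 60 msec above Baseline. The site draws PK, potassium and magnesium samples, repeats the ECG within 30 minutes, informs the Medical Monitor and holds the drug: "Patient study treatment dosing should be interrupted until the results of the centrally read cardiologist report are received". The rule ends there.

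The heading of 7.2.2 names drug discontinuation, although the section sits within 7.2, Temporary Discontinuation. Section 8.2.3 sends the reader to 7.2 for QTc withdrawal criteria. Section 8.5 also speaks of ECG withdrawal criteria, but points to 7.1.1, which is Liver Function.

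The rules in 7.1 read differently:
- Liver: "Study intervention will be discontinued for a patient if liver chemistry stopping criteria are met and confirmed upon repeat testing".
- Neutrophils: "Withdraw study treatment if absolute neutrophil count drops below 500" cells/mm³, if a confirmatory sample agrees.
- CK: withdraw for a value above 5 x ULN that "is observed on repeat testing without benign explanation".
- Skin: "Withdraw study treatment in the case of any severe skin reaction which is considered to be related to the study treatment".

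The end of 7.1.4 adds: "If drug is stopped for reasons as described above, restarting the study drug is not allowed".

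On restarting, 7.3 limits rechallenge to circumstances given in 7.2. The only express permission there is in 7.2.1, which opens "If a drug is stopped temporarily due to a clearly unrelated adverse event" and gives COVID-19 infection as an example.

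**The concern.** A stopping rule normally has three parts: a trigger, a confirmation step and a consequence. Section 7.2.2 has the first two. Read literally, the hold lapses when the report arrives, even if the report confirms a QTcF above 500 msec.

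The protocol treats QT as a safety focus. It excludes a Baseline mean QTcF above 450 msec, a personal or family history of congenital long QT syndrome, and uncontrolled low potassium or magnesium. A patient at 451 msec at Baseline is ineligible, while a patient centrally confirmed at 501 msec on treatment has no stated stop.

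What is at stake is patient safety and consistency of handling. About 20 sites could treat the same confirmed finding differently.

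**Working it through.** There is no power or error-rate figure to reproduce. The check is a comparison of text, plus two small counts.

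**1. The dosing rules side by side**

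| Section | Trigger | Confirmation | Stated outcome |
|---|---|---|---|
| 7.1.1 | Liver chemistry criteria (algorithm figure not visible) | Repeat testing | Discontinue |
| 7.1.2 | Neutrophils <500 cells/mm³ | Confirmatory sample | Withdraw |
| 7.1.3 | CK >5 x ULN | Repeat testing, no benign explanation | Withdraw |
| 7.1.4 | Severe skin reaction judged related | None stated | Withdraw |
| 7.2.2 | QTcF >500 msec | Repeat ECG, central read | None stated |
| 7.2.2 | QTcF rise >60 msec | Repeat ECG, central read | None stated |

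A stop is stated for 4 of 4 rules in 7.1 and for 0 of 2 criteria in 7.2.2.

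**2. Does other visible text supply the outcome?**
- 7.1 lists liver, neutrophil, CK and skin criteria. ECG is not among them.
- 7.2.1 makes a dosing gap above 21 days permanent. That limit depends on time, not on the QTcF result.
- 7.3 refers back to 7.2 and adds no QTcF condition.
- 8.0 has immediate safety concerns discussed with the Medical Monitor to settle whether treatment continues. This names a decision process but no QTcF threshold.
- 7.4 lets the Investigator withdraw a patient in the patient's interest. It is discretionary.
- 8.3.3 requires non-serious AESIs to be followed until resolution, stabilization or explanation. This is follow-up, not a dosing rule.
- 9.6 has the DSMB review unblinded safety data. It sets no rule for an individual patient.
- SAP 5.5.1 and 5.5.3 use the same two thresholds for reporting only.

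None says which central result releases the hold or ends treatment.

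**3. How often the criteria are checked** (Schedule of Assessments, footnote a)

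Triplicate sets after the first dose: Day 1 at 2 h (1) + Day 8 predose and 2 h (2) + Days 15, 29, 43, 57 and 85 (5) = 8. A patient not fasting on Days 1 and 8 adds 2, giving 10. The Day 85 set follows the last dose, so 8 − 1 = 7 sets (10 − 1 = 9 if not fasting) can affect dosing.

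Nominal days to the next scheduled ECG visit: 8−1 = 7; 15−8 = 7; 29−15 = 14; 43−29 = 14; 57−43 = 14; 85−57 = 28. The longest scheduled interval is 28 days.

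**4. Does AESI status imply a stop?**

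SAP 5.5.1 states "Adverse events of special interest (AESI) are captured on the AE eCRF page and include the following events" and lists five. CK and severe related skin reaction have a stop at the AESI threshold. Mouth ulceration has no rule, neutrophils are an AESI below 1000 but stop treatment only below 500, and QTcF has no stated outcome. So 3 of 5 AESIs have no stated stop at their AESI threshold. AESI status therefore does not show that a QTcF stop was intended. The heading of 7.2.2 and the wording of 8.2.3 and 8.5 are the better evidence.

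**The case against.** The strongest reply is that the decision step exists. Section 7.2.2 brings in the Medical Monitor, and 8.0 gives the Medical Monitor discussion the task of settling whether the patient continues. Case-by-case judgment after a cardiologist's read is a defensible design. The text also leans against restart: the heading and cross-references speak of discontinuation or withdrawal, 7.3 allows rechallenge only in limited circumstances, and the sole express permission concerns clearly unrelated events or COVID-19.

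Much of this stands. A reader might infer that the protocol tells sites to re-dose after a confirmed QTcF above 500 msec. It does not: no passage orders re-dosing. A reader might also infer that such a patient could go 28 days without an ECG. The documents do not support that either. Footnote i of the Schedule of Assessments allows unscheduled visits to repeat assessments or for safety follow-up, 8.2.3 anticipates additional QTc readings, and 8.3.3 requires AESI follow-up. The 28 days is only the longest interval between scheduled visits.

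The contrast with 7.1 also has limits. The CK and skin rules turn on clinical judgment, and the liver algorithm cannot be checked here.

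What remains is that 7.2.2 is labelled a discontinuation criterion, ends its hold on receipt of a report, and never links the result to dosing. The general clauses say who may decide. They do not say that a confirmed value keeps the hold in place.

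**Conclusion.** The gap is real but minor. On the visible text, neither ECG criterion has a stated condition for resuming or stopping, and the wording that ends the hold is wrong for a centrally confirmed QTcF above 500 msec. The decision is left to the general provisions in 8.0 and 7.4.

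The number of patients affected is unknown; the documents give no event rate and none is assumed. The efficacy analysis is unaffected, because SAP 5.4.1.5 already treats discontinuation of study treatment for any reason as an intercurrent event.

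The conclusion rests on visible text only. The contents of the protocol's AESI section (8.3.6) and the appendices are not available, so a rule there cannot be excluded. Section 7.2.2 refers to neither. The wrong cross-reference in 8.5 is clerical and stands regardless.

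**What to change.** In Protocol 7.2.2, replace the release on receipt with a release that depends on the result:
1. Dosing stays held until the Investigator and Medical Monitor have reviewed the central read.
2. If the central read confirms neither criterion, dosing may resume.
3. If it confirms QTcF above 500 msec, discontinue permanently.
4. If it confirms a rise above 60 msec with QTcF at or below 500 msec, the Medical Monitor decides and documents the decision. The potassium and magnesium results that 7.2.2 already collects, and the correction that 8.2.4 already requires, would inform it.

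In 8.5, change the cross-reference from 7.1.1 to 7.2.2.

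The split between items 3 and 4 is a clinical proposal, not something the documents dictate. A sponsor may prefer another line, provided the section states what the central result means for dosing.

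The cost is wording only, with no added visits, tests or patients. The downside is possibly a few more permanent discontinuations, including some with a correctable cause such as low potassium. SAP 5.4.1.5 already covers these.

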7.3 Rechallenge

Rechallenge is allowed in only limited circumstances when the drug is temporarily stopped, as noted in [Section 7.2](#). Once the drug is permanently stopped, no rechallenge is allowed.

7.4 Patient Discontinuation/Withdrawal from the Study

All patients will be advised that they are free to withdraw from participation in the study at any time, for any reason, and without prejudice. The Investigator also has the right to withdraw patients from the study at any time for lack of therapeutic effect that is intolerable or otherwise unacceptable to the patient, for intolerable or unacceptable AEs, intercurrent illness, noncompliance, with study procedures, administrative reasons, or in the Investigator's opinion, to protect the patient's best interest. The Sponsor reserves the right to request the withdrawal of a patient due to protocol violations or other reasons.

- Although a patient is not obliged to give his/her reason(s) for withdrawing prematurely from a study, the Investigator should make a reasonable effort to ascertain the reason(s), while fully respecting the patient's rights.
- If the patient withdraws consent, the Investigator must clearly determine and document if the patient is making a full and immediate revocation of consent (eg, no additional data collection may occur) or if the patient is willing to proceed with additional study procedures

to ensure a safe and orderly discharge from the study (eg, completion of Early Termination and EOS Visits).

- If the patient withdraws consent for disclosure of future information, the Sponsor may retain and continue to use any data collected before such a withdrawal of consent.
- If a patient withdraws from the study, he/she may request destruction of any samples taken and not tested, and the Investigator must document this in the study center study records.
- If there is a medical reason for withdrawal, the patient should remain under the supervision of the Investigator until satisfactory health has returned.
- See the SoA ([Table 1](#)) for data to be collected at the time of study discontinuation and follow-up and for any further evaluations that need to be completed.

7.5 Lost to Follow-up

A patient will be considered lost to follow-up if he or she repeatedly fails to return for scheduled visits and is unable to be contacted by the study center.

The following actions must be taken if a patient fails to return to the clinic for a required study visit:

- The study center must attempt to contact the patient and reschedule the missed visit as soon as possible and counsel the patient on the importance of maintaining the assigned visit schedule and ascertain whether or not the patient wishes to and/or should continue in the study.
- Before a patient is deemed lost to follow-up, the Investigator or designee must make every effort to regain contact with the patient (where possible, 3 telephone calls and, if necessary, a certified letter to the patient's last known mailing address or local equivalent methods). These contact attempts should be documented in the patient's medical record.
- Should the patient continue to be unreachable, he/she will be considered to have withdrawn from the study and the last known contact/assessment will be the date of discontinuation.

